## 7.1.1 Molecular pre-screening

Evidence of genetic alterations, including FGFR2 gene fusion or other FGFR genetic alterations, can be obtained from pre-existing analysis, local testing of samples at an institution-designated laboratory or an institution-designated sequencing facility, or through the submission of samples to a QED Therapeutics designated laboratory central facility for testing. When possible, pre-existing analysis by local testing should be performed using a clinically validated test in a CLIA-certified (or equivalent) laboratory.

If local or central testing will be conducted to determine the molecular status of the tumor, potential patients will be asked to sign a pre-screening informed consent to allow for the collection and analysis of the sample. A pre-screening consent form is not needed if the molecular status of the tumor was previously determined. Written documentation of the local FGFR2 test result must be present in the source documentation for review by QED Therapeutics.

For central FGFR molecular testing, the archival or newly obtained tumor sample will be sent to a QED Therapeutics designated lab and the results of the analysis will be communicated to the respective center. Upon positive determination that the sample submitted contains the required FGFR2 gene fusions or translocation (Cohorts 1 and 3), or FGFR1, 2, or 3 activating mutation or FGFR1 or 3 fusions or translocations (Cohort 2), the patient may sign the study's main Informed Consent to begin screening procedures.

Additional testing will be performed to evaluate other genetic alterations related to or thought to be related to cholangiocarcinoma.

A copy of the corresponding pathology report for each set of slides/blocks should be sent to QED Therapeutics designated central laboratory.

FGFR translocation/alterations status must be captured on the appropriate eCRF upon enrollment onto the study after the patient has signed the study's main Informed Consent.

The tumor blocks will be returned, if molecular pre-screening inclusion criteria are not met.

#### 7.1.2 Screening

The IRB/IEC study approved informed consent form (ICF) must be signed and dated before any study-specific screening procedure is performed. Procedures which are part of the clinical routine during the initial diagnostic work-up of the patient may be obtained before obtaining the ICF. A copy of the ICF must be given to the patient or to the person signing the form. The investigator or designee must record the date when the study informed consent was signed in the medical records of the patient.

Patients will be evaluated against study inclusion and exclusion criteria and safety assessments. For details of assessments, refer to Table 7. Screening assessments must be

completed within 21 days prior to the first dose of treatment except for (1) the radiological tumor assessment, which should be performed within 28 days prior to the first dose, and (2) the ophthalmology examination, which should be completed within 14 days prior to first dose. Screening assessments must be repeated if outside of screening windows.

## 7.1.2.1 Eligibility screening

After a patient signs the study Informed Consent Form, the investigator or clinical site should determine patient eligibility.

#### 7.1.2.2 Information to be collected for screen failures

Patients who signed a molecular pre-screening ICF but are considered as ineligible after molecular screening, as well as patients who are found not eligible after signing the informed consent form to participate in the treatment phase of the study, will be considered as screening failures, and data will be handled in the same manner. The reason for not being started on study treatment will be entered on the screening phase disposition page. For all screening failure patients, demography, inclusion/exclusion and informed consent information along with the reason for screen failure will be collected. No other data will be entered in the database for patients who are screen failures, unless the patient experienced a Serious Adverse Event during the screening phase (see Section 8 for SAE reporting details). For molecular prescreening failures, only SAEs possibly related to a study procedure will be reported.

## 7.1.2.3 Patient demographics and other baseline characteristics

Data to be collected will include general patient demographics, relevant medical history and current medical conditions, prior concomitant medications, diagnosis and extent of tumor, baseline tumor mutation status (FGFR gene fusions or translocation or other FGFR genetic alterations) and details on prior antineoplastic treatments.

## 7.1.3 Treatment period

The treatment period commences on the first day of the first cycle of BGJ398 and ends after the last dose of BGJ398.

During the study treatment period, patients will be regularly monitored to assess the safety and early anti-tumor activity of treatment. For purpose of scheduling and evaluations, a treatment cycle will consist of 28 days.

During the treatment period, the patient is obliged to follow the investigators instructions with regards to contraception, concomitant medications and dosing regimen. There is no fixed duration; patients may continue treatment with the study drug until the development of an unacceptable toxicity that precludes any further treatment, disease progression, and/or treatment is discontinued at the discretion of the Investigator or by patient refusal. For details of assessments during the treatment period, refer to Table 7.

## 7.1.4 Discontinuation of study treatment

Patients may voluntarily discontinue from the study treatment for any reason at any time. If a patient decides to discontinue from the study treatment, the investigator should make a reasonable effort (e.g. telephone, e-mail, letter) to understand the primary reason for this decision and record this information in the patient's chart and on the appropriate CRF pages. They may be considered withdrawn if they state an intention to withdraw, fail to return for visits, or become lost to follow-up for any other reason.

Study treatment must be discontinued under the following circumstances:

- Adverse events that lead to substantial changes in individual risk-benefit considerations
- Dose delay of > 14 days from the intended day of the next scheduled dose, unless otherwise specified in Section 6.2.1, and approval by QED Therapeutics' medical monitor
- Pregnancy
- Protocol deviation that results in a significant risk to the patient's safety

Patients who discontinue study treatment should NOT be considered withdrawn from the study. They should return for the assessments indicated in Table 7 (end of study treatment visit) and then enter the follow-up epoch. If they fail to return for these assessments for unknown reasons, every effort (e.g. telephone, email, letter) should be made to contact them as specified in Section 7.1.7 (Lost to follow-up).

For patients who discontinue treatment for reasons other than documented disease progression, death, lost to follow-up, or withdrawal of consent, tumor assessments must continue to be performed every 8 weeks until documented disease progression, death, lost to follow-up, or withdrawal of consent.

For patients who have documented radiographic disease progression and continue study treatment according to Section 6.2.1, no further imaging or transmittal of images for central imaging assessment is required.

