# Disease progression follow-up period

All patients enrolled in the study who discontinue study treatment for any reason other than disease progression will have a tumor assessment every 8 weeks, until disease progression or the initiation of subsequent anticancer therapies, or death, whichever occurs first

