## 7.2 Assessment types

## 7.2.1 Efficacy assessment

Tumor response will be evaluated locally by the investigator according to the guideline (see Appendix 3) based on the Response Evaluation Criteria in Solid Tumors (RECIST) Version 1.1 (Eisenhauer 2009). Each patient will be evaluated for all potential sites of tumor lesions at screening/baseline and every 8 weeks after starting study treatment until disease progression.

CT (Computed Tomography) /MRI (Magnetic Resonance Imaging) scans will be performed at baseline within 28 days before start of treatment and subsequently every 8 weeks from treatment start until progression of disease.

After baseline, the first assessment should be performed at Cycle 3 Day 1 ( $\pm$ 7 day window) and all subsequent assessments should be performed within  $\pm$ 7 days of the scheduled day of assessment. The same method of assessment and the same technique should be used to characterize each individual and reported lesion at baseline and during follow-up. If a patient discontinues treatment for reasons other than radiological documentation of progression of disease, an efficacy assessment should be performed at the time of End of Treatment unless a CT/MRI for tumor measurement was performed  $\leq$  4 weeks earlier.

Chest, abdomen, and pelvis CT scans are required for all patients at baseline. If at baseline, a patient is known to have a contraindication to CT i.v. contrast media or develops a contraindication during the trial, a contrast-enhanced MRI (if possible) of chest, abdomen, and pelvis should be performed. CT/MRI of the brain should be performed if clinically indicated.

For the patients with skeletal lesions suspected at baseline, whole-body bone imaging should be obtained either with a TC99 bone scan or alternatively a NaF CT/ MRI PET scan. Of note, the CT or MRI portion of the scan should only be substituted for the required chest, abdomen, and pelvic CT scans if the CT or MRI is of diagnostic quality and meets all requirements as described in the study imaging guide (ie, oral and IV contrast, slice thickness, and anatomic coverage). Post-baseline, if skeletal lesions were identified at baseline, which are not visible on the chest, abdomen or pelvis CT/MRI scan, bone imaging with either a TC99 bone scan or NaF CT/MRI PET is required at all post-baseline imaging timepoints (every 8 weeks). In all cases that post-baseline bone

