Compliance to the study treatment will be summarized in terms of the RDI or percentage of patients who took a predefined percentage of the number of prescribed. The predefined RDI categories are ≤ 0.5 , $>0.5 - \leq 0.75$, $>0.75 - \leq 0.9$, $>0.9 - \leq 1.0$ and >1.0 . The number and proportion of patients falling in each category will be presented. Details are provided in Section [2.5.1](#).

2.6 *Analysis of the primary objective*

2.6.1 *Variable*

For Cohort 1, the primary objective of the study is to assess anti-tumor activity of infigratinib using overall response rate assessed by central imaging review.

Best overall response (BOR) is the best overall response a subject ever achieves during the study prior to any subsequent anti-cancer therapy. Overall response rate (ORR) is defined as the proportion of patients with a best overall response of confirmed Complete Response (CR) or Partial Response (PR), as per RECIST version 1.1, among the corresponding analysis set.

ORR (central imaging assessment) is the primary efficacy endpoint, and its analysis consists of a Clopper-Pearson 95% CI accompanied by a characterization of time to response (TTR) and duration of response (DOR) to allow for a more complete characterization of the beneficial effect Infigratinib may have in the principal analysis population. The Brookmeyer-Crowley method will be used to construct the 95% CI for each of TTR and DOR.

2.6.2 *Statistical Hypothesis, Model, and Method of Analysis*

For Cohort 1, the primary analysis of the primary endpoint (ORR assessed by central imaging review) should occur when all subjects in Cohort 1 have the potential to be followed for at least 10 months after their initial exposure to study treatment. The formal interim analysis for Cohort 1 will be conducted when all patients in the interim efficacy analysis set have been followed for at least 10 months after their initial exposure to the study treatment. Any confirmed PR or CR until the data cut-off date and any subsequent anti-cancer therapy will be considered as a responder for ORR, irrespective of when it occurred.

2.7 *Analysis of Secondary Objective(s)*

This section describes analyses of secondary objectives for Cohort 1. The same endpoints will be analyzed for Cohorts 2 and 3 as exploratory, so the approaches described in this section also apply to Cohort 2 and 3.

2.7.1 *Secondary Efficacy Objectives*

Overall Response Rate Per Investigator

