ORR per investigator is among the secondary endpoints. The estimated ORR will be presented with the corresponding 95% confidence interval based on exact binomial distribution using the corresponding analysis set.

Overall Survival

Overall Survival (OS) is defined as the time from the date of start of treatment to the date of death due to any cause. The survival time for subjects without documentation of death prior to the data cutoff will be censored at the last date the subject was known to be alive prior to the cutoff date. Survival time for subjects with no post-baseline survival information will be censored at the date of start of treatment.

OS will be analyzed using the Kaplan-Meier method. Survival rate at 4, 6, 8, 12, 18, 24 months (and every 6 months thereafter as reported in database) with median OS will be estimated along with 95% confidence intervals.

Progression Free Survival

Progression free survival (PFS) is defined as the date of the start of treatment to the date of the event defined as the first documented progression or death due to any cause, whichever is earlier. If subject has not had an event, progression-free-survival is censored at date of last valid tumor assessment or start of study treatment if there is no valid tumor assessment available. For subjects who had an event after two or more missed visits, the subject will be censored at the last adequate tumor assessment. The PFS analyses will be done based on central and local assessments separately. Kaplan-Meier analysis of PFS will be provided.

The primary PFS will be derived based on all the tumor assessments and death including any after a subsequent anti-cancer therapy. A sensitivity analysis will also be conducted on PFS excluding the tumor assessments and death after any subsequent anti-cancer therapies. If the event (the first progressive disease or death) is after a subsequent anti-cancer therapy, the PFS for the sensitivity analysis will be censored at the last valid tumor assessment prior to all subsequent anti-tumor therapies or first dose date if there is no valid tumor assessment prior to all subsequent anti-tumor therapies.

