For Cohorts 2 and 3, the percentage of subjects who are progression-free at the second scheduled scan (approximately 16 weeks from treatment initiation) or later will be analyzed using 95% exact binomial confidence interval. Patients who do not have scans to show that they are progression-free at the second scheduled scan or later will be considered as not benefiting from the study treatment. Sensitivity analysis will be done by estimating PFS >16 weeks using K-M estimate.

Best Overall Response and Disease Control Rate

Overall lesion assessments will be listed by subject. BOR will be summarized for the rate of best overall response of progressive disease, stable disease, confirmed partial response (PR), and confirmed complete response (CR) separately; it will also be summarized for the Disease Control Rate which are the proportion of subjects having respectively a best overall response of confirmed PR or CR, or stable disease. The estimates will be presented along with the corresponding 95% exact confidence interval. Best overall response will be provided for investigator assessment and central assessment as specified by cohort (Section 1.2). In addition, the concordance of best overall response based on central assessment and local assessment will be assessed.

Best tumor burden change (maximum tumor burden reduction from baseline or minimum tumor burden increase from baseline if tumor burden has never reduced prior to any anti-cancer therapy) will be presented graphically.

Response Onset and Duration of Response

Response onset will be estimated using Kaplan-Meier product limit method to analyze TTR based on ORR central imaging assessment. The Brookmeyer-Crowley method will be used to construct the 95% CI for TTR. DOR will be further summarized by length of exposure to

infigratinib using the following exposure cut-off lengths: at least 6 months, at least 9 months, at least 12 months.

Response onset and duration of response (DOR) will be summarized for confirmed responders only, based on local and central assessments separately. Response onset is defined as the time from the first study drug administration date to the initial response date. DOR is defined as the time from the initial response to the date of the event defined as the first documented progression or death due to any cause, whichever is earlier. The same event/censoring rule applied to PFS will be applied to DOR.

2.7.2 *Safety Objectives*

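### Cohort 1 scans stop at a locally judged progression, so central DOR and PFS may be censored informatively, and no planned analysis tests this within the central read

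*Protocol*

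**What the plan says.** **Who calls progression, and when scans stop.** Protocol 7.2.1: "Tumor response will be evaluated locally by the investigator according to the guideline". CT/MRI is done at baseline and "subsequently every 8 weeks from treatment start until progression of disease". After treatment ends, the disease progression follow-up paragraphs (Protocol 4.1 and 7.1.6) provide scans only for patients "who discontinue study treatment for any reason other than disease progression will have a tumor assessment every 8 weeks". For patients who stay on drug after documented radiographic progression, Protocol 7.1.4 says that "no further imaging or transmittal of images for central imaging assessment is required". Protocol 7.2.1 sends all Cohort 1 images that are obtained to the central imaging CRO. Neither document asks for central agreement on progression before scanning ends.

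**What the central read is used for.** Central ORR is the primary endpoint, and SAP 2.6.1 reports time to response and DOR alongside it. SAP 2.7.1 analyses PFS and DOR on central and on local assessments separately.

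**Censoring (SAP 2.7.1).** Without an event, "progression-free-survival is censored at date of last valid tumor assessment". An event that follows two or more missed visits is censored back to the last adequate assessment. For DOR: "The same event/censoring rule applied to PFS will be applied to DOR". Deaths count in the primary PFS, including those after new anticancer therapy. The one stated PFS sensitivity analysis removes assessments and deaths after new therapy. Central-local concordance is planned for best overall response only.

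**The concern.** Suppose the investigator calls progression and the central reader does not. Scheduled scanning is over, so the central reader will probably never see a later progression. The patient is censored in central DOR and PFS at the scan on which the investigator saw growth. Kaplan-Meier treats censored patients as having the same future risk as those still followed. Patients whose investigator has just seen growth plausibly have a higher risk. If so, the central curve sits too high.

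Central DOR is the durability evidence that accompanies the primary endpoint in a single-arm trial. There is no comparator arm in which such a bias could cancel.

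**Working it through.** **1. The plan's own figures.** The documents give none for DOR, for reader disagreement on progression, or for censoring. The only Cohort 1 precision figures concern ORR: the maximum exact half-width is 9.87% for n=106 (stated: not above 10%) and 12.02% for n=72 (stated: not above 12%; agrees on rounding). They do not bear on this point.

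**2. Path of a patient with local but no central progression.**
- Scheduled scans end at the local call (Protocol 4.1, 7.1.6, 7.2.1; 7.1.4 if still on drug).
- No central event has been recorded, so the patient is censored at the last valid scan (SAP 2.7.1).
- Exception: a death before two missed visits is an event. With 8-weekly scans this window is about 2 × 8 = 16 weeks.
- Counting assessments after new therapy seldom helps, because none are scheduled. The sensitivity analysis that drops them censors more, not less.

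**3. Size under stated assumptions.** Simulated Kaplan-Meier central DOR, 200,000 responders per setting.
- From the documents: scans every 56 days (±7 days), censoring at the last scan, and a death within 16 weeks plus 7 days of it counted as an event.
- Assumed: exponential time to central progression with median 4, 6 or 8 months. The early-data median PFS of 175 days in the Amendment 2 rationale (175/30.4375 = 5.7 months) lies within that range.
- Assumed: a fraction q of 10-40% designated for a local call one or two scans before central progression. The share actually called early is lower, because the patient must have been followed that long; for q=40%, one scan and median 6 months it is 32%, with 25% ending censored.
- Assumed: median survival of 8 months after progression.

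Each cell compares scanning continued to central progression → scanning stopped at the local call.

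| Median (months) | Lead (scans) | q | 6-month DOR, % | 12-month DOR, % | KM median, months |
|---|---|---|---|---|---|
| 4 | 1 | 10% | 38.3 → 39.8 | 14.5 → 15.9 | 5.4 → 5.4 |
| 4 | 1 | 40% | 38.2 → 45.0 | 14.7 → 21.6 | 5.4 → 5.5 |
| 6 | 1 | 10% | 52.7 → 54.2 | 27.9 → 29.8 | 7.2 → 7.3 |
| 6 | 1 | 40% | 52.7 → 59.3 | 27.8 → 36.9 | 7.2 → 8.7 |
| 8 | 1 | 40% | 62.1 → 68.2 | 38.4 → 47.9 | 9.1 → 11.1 |
| 4 | 2 | 10% | 38.3 → 38.4 | 14.8 → 15.5 | 5.4 → 5.3 |
| 4 | 2 | 40% | 38.4 → 39.1 | 14.7 → 18.7 | 5.4 → 4.2 |
| 8 | 2 | 40% | 61.7 → 63.7 | 38.2 → 45.3 | 9.1 → 10.8 |

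Over all 24 settings, 12-month DOR rises by 0.7 points (15.5 − 14.8) to 9.5 points (47.9 − 38.4). The 6-month rise is 1.4 to 6.8 points with a one-scan lead and 0.1 to 2.0 with two. The median moves by 0 to +2.0 months with one scan and by −1.2 to +1.7 with two.

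**4. Sensitivity.** With q=30%, a one-scan lead and median 6 months, post-progression survival of 4, 8 or 12 months gives a 12-month excess of 5.0, 6.5 or 7.1 points. If local calls are unrelated to central progression (5% or 10% chance per scan), 12-month DOR goes from 27.8% to 26.7% or 25.5%. That is slightly lower, because early deaths stay as events while survivors are censored back.

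**The case against.** **Scope of the sentence in 7.1.4.** A reader might infer that it ends imaging for everyone at the investigator's call. It does not. It opens "For patients who have documented radiographic disease progression and continue study treatment according to Section 6.2.1, no further imaging or transmittal of images" and names no reader. Since Protocol 4.1, 6.1.3 and 7.1.3 run treatment until progression, that group may be nearly empty. This stands. For other patients the stop rests on 4.1, 7.1.6 and 7.2.1.

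**Direction and a simpler calculation.** A reader might infer that central DOR is certainly inflated, and by more than shown above. With deaths ignored and a one-scan lead in a fraction d, the per-scan hazard p becomes (1−d)p/(1−dp). For a 5-month median, p = 0.225 and three scans fall within 6 months. The 6-month DOR then goes from 0.465 to 0.574 at d=30%. For an 8-month median, 12-month DOR goes from 0.384 to 0.504. These values are too high. They leave out deaths, which the SAP counts. They also censor some responders at time zero; with scanning stopped there, the response could not be confirmed, and DOR covers confirmed responders only. Leaving those patients as events gives 0.535 and 0.482, still before deaths are counted.

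**Local analyses.** PFS and DOR on local assessment count these progressions, so a central-local difference would be visible. This is fair, but partial. That difference mixes all reader disagreement and does not show what the central estimate would be if these patients were events.

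**Missed visits.** The SAP does not say whether scans no longer required count as missed. If they do not, later deaths become events. That does not remove the issue: central PFS time is the earlier of central progression and death, so dating the event at death can only match or exceed it.

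**Unseen detail.** The imaging CRO's site manual might contain a confirmation step. Protocol and SAP state none.

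**Weight.** Central ORR is not affected by this mechanism, and no hypothesis or threshold attaches to DOR. Both are true, and they keep this a modest point.

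**Conclusion.** The gap is real and limited. Scheduled Cohort 1 scans stop on a local progression call. Central DOR and PFS then censor at the last valid scan unless a death counts, and no planned analysis tests local progression without central progression inside the central read.

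Upward bias is likely if local calls come shortly before central progression. The documents do not establish it, because they give no discordance rate. With 10-40% of responders designated for a call one or two scans early, underlying medians of 4 to 8 months and deaths counted by the SAP rule, 12-month DOR is raised by about 1 to 9.5 points. The effect on the median is mixed, and there is no upward bias if the calls are unrelated. The range illustrates the size and is not an estimate for this trial.

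A cross-reference also fails. Protocol 7.1.4 cites 6.2.1 for treatment after progression. Section 6.2.1 deals with dose modification and delay and has no such provision, while 4.1, 6.1.3 and 7.1.3 run treatment until progression.

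**What to change.** SAP 2.7.1: add a sensitivity analysis of central DOR and central PFS. A patient who is censored centrally at or after investigator progression counts as an event at the investigator's progression date. Report how many such patients there are for each endpoint.

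The cost is one more analysis and a count, on data already collected, plus a possibly less favourable supportive DOR figure. SAP Section 1 provides for changes by amendment or addendum.

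Protocol 7.1.4 must be reconciled with 6.2.1 and with the treatment-duration passages in 4.1, 6.1.3 and 7.1.3. No new imaging rule is proposed for patients treated beyond progression, because the documents first need to settle whether that pathway exists.
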